### 4.6.2 Discontinuation from the Study

Women and their infants have the right to voluntarily withdraw from the study at any time for any reason. In addition, the investigator has the right to withdraw a woman from the study at any time. Women who decide to discontinue the study (this includes discontinuation of either the mother or the infant; this does not apply to treatment discontinuation as described in Section 3.1.4) will be invited to attend an early study discontinuation visit as soon as possible (further details in Section 3.1.5).

Reasons for women's discontinuation from the study may include, but are not limited to, the following:

- Woman's withdrawal of consent
- Study termination or site closure
- AE
- Loss to follow-up
- Any medical condition that the investigator or Sponsor determines may jeopardize the woman's or infant's safety if he or she continues in the study
- Woman's non-compliance, defined as failure to comply with protocol requirements as determined by the investigator or Sponsor

Every effort should be made to obtain a reason for the woman's discontinuation from the study. The primary reason for discontinuation from the study should be

documented on the appropriate eCRF (see Section 3.1.5). Women who withdraw from the study will not be replaced.

### 4.6.3 **Study Discontinuation**

The Sponsor has the right to terminate this study at any time. Reasons for terminating the study may include, but are not limited to, the following:

- The incidence or severity of adverse events in this or other studies indicates a
  potential health hazard to women in the study.
- Enrolment is unsatisfactory.

The Sponsor will notify the investigator if the Sponsor decides to discontinue the study.

### 4.6.4 Site Discontinuation

The Sponsor has the right to close a site at any time. Reasons for closing a site may include, but are not limited to, the following:

- Excessively slow recruitment
- Poor protocol adherence
- Inaccurate or incomplete data recording
- Non-compliance with the International Council on Harmonisation of Technical Requirements for Registration of Pharmaceuticals for Human Use (ICH) guideline for GCP
- No study activity (i.e., all women and their infants have completed the study and all obligations have been fulfilled)

### 5. ASSESSMENT OF SAFETY

### 5.1 SAFETY REPORTING REQUIREMENTS FOR STUDIED MEDICINAL PRODUCTS

### 5.1.1 Safety Parameters and Definitions

The reporting requirements in this section apply to ocrelizumab and any other treatments used as co-administered products (i.e., premedication), according to the label. For a list of products, see Section 4.3.

For safety reporting requirements for non-studied medicinal products, see Section 5.2.

Safety assessments will consist of monitoring and recording serious adverse events and non-serious adverse events (including adverse events of special interest), performing safety laboratory assessments, measuring vital signs, and conducting other tests that are deemed critical to the safety evaluation of the study as per standard medical practice.

### 5.1.1.1 Adverse Events

According to the ICH, an adverse event is any untoward medical occurrence in a subject or clinical investigation patient administered a pharmaceutical product, regardless of causal attribution. An adverse event can therefore be any of the following:

- Any unfavorable and unintended sign (including an abnormal laboratory finding), symptom, or disease temporally associated with the use of a medicinal product, whether or not considered related to the medicinal product
- Any new disease or exacerbation of an existing disease (a worsening in the character, frequency, or severity of a known condition), except as described in Appendix 5
- Recurrence of an intermittent medical condition (e.g., headache) not present at baseline
- Any deterioration in a laboratory value or other clinical test (e.g., ECG, X-ray) that is
  associated with symptoms or leads to a change in study treatment or concomitant
  treatment or discontinuation from study medicine

# 5.1.1.2 Assessment of Serious Adverse Events and Non-Serious Adverse Events of Special Interest (Immediately Reportable to the Sponsor) and Other Non-Serious Adverse Events

### **Serious Adverse Events**

A serious adverse event is any adverse event that meets any of the following criteria:

- Is fatal (i.e., the adverse event actually causes or leads to death)
- Is life-threatening (NOTE: The term "life-threatening" refers to an event in which the patient was at immediate risk of death at the time of the event; it does not refer to an event that hypothetically might have caused death if it were more severe)
- Requires or prolongs inpatient hospitalization
- Results in persistent or significant disability/incapacity (i.e., the adverse event results in substantial disruption of the patient's ability to conduct normal life functions)
- Is a congenital anomaly/birth defect in a neonate/infant born to a mother exposed to study medicine
- Is a significant medical event in the physician's judgment (e.g., may jeopardize the patient or may require medical/surgical intervention to prevent one of the outcomes listed above).

The terms "severe" and "serious" are not synonymous. Severity refers to the intensity of an adverse event (e.g., rated as mild, moderate, or severe, or according to National Cancer Institute Common Terminology Criteria for Adverse Events [NCI CTCAE] criteria; see Appendix 5); the event itself may be of relatively minor medical significance (such as severe headache without any further findings).

Severity and seriousness need to be independently assessed for each adverse event recorded on the eCRF (for detailed instructions, see Appendix 5).

### Non-Serious Adverse Events of Special Interest

Adverse events of special interest (AESI) for this study include the following:

- Cases of potential medicine-induced liver injury that include an elevated ALT or AST in combination with either an elevated bilirubin or clinical jaundice, as defined by Hy's law (see Appendix 5).
- Suspected transmission of an infectious agent by the study medicine, as defined below:
  - Any organism, virus, or infectious particle (e.g., prion protein transmitting transmissible spongiform encephalopathy), pathogenic or non-pathogenic, is considered an infectious agent. A transmission of an infectious agent may be suspected from clinical symptoms or laboratory findings that indicate an infection in a patient exposed to a medicinal product. This term only applies when a contamination of the study medicine is suspected.

### Non-Serious Adverse Events other than Adverse Events of Special Interest

All non-serious adverse events (in addition to adverse events of special interest) must be collected for this study, and coded according to the appropriate level of Medical Dictionary for Regulatory Activities (MedDRA) classification.

### Specific Adverse Events that are Exempt from Collection

Adverse events and serious adverse events related to MS are not considered for recording in the eCRF. Medical occurrences or symptoms of deterioration that are anticipated as part of MS or which are expected in the patient population studied should be recorded as an adverse event only if judged by the physician to have unexpectedly worsened in severity or frequency or changed in nature at any time during the study.

Following the above rationale, the following events will not be considered as adverse events for this study:

- 1. MS relapses.
- 2. Disability progression (increase in EDSS or other scales performed by the physician).
- MRI activity (new/enlarged T2 or T1 gadolinium-enhancing lesion in spinal or brain MRI), unless the activity is suggestive of a serious adverse event such as PML. In this case, information should be recorded in the section "PML" of the eCRF.
- 4. MS signs and symptoms.

Although these adverse events are not being actively solicited, the investigator/patients are reminded of the possibility to report any adverse reactions (for which they suspect a causal role of a medicinal product) that come to their attention to the Sponsor of the suspected medicinal product, or to the concerned competent authorities via the national spontaneous reporting system.

Ocrelizumab—F. Hoffmann-La Roche Ltd 54/Protocol MN42989, Version 4 (United States)

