### 4.5.2.5 Assessment of Relapses

Potential relapses should be recorded throughout the treatment period. See Appendix 1 (Schedule of Assessments) for the timing of these assessments.

All new or worsening neurological events consistent with MS representing a "clinical relapse" are to be reported on the dedicated "MS relapse" form. A clinical relapse is defined as a monophasic clinical episode with patient-reported symptoms and objective findings typical of MS, reflecting a focal or multifocal inflammatory demyelinating event in the CNS, developing acutely or sub-acutely, with a duration of at least 24 hours, with or without recovery, and in the absence of fever or infection (Thompson et al. 2018). MS relapses should not be reported as an adverse event, unless they are serious.

It is recommended that women with new neurological symptoms suggestive of a relapse have an EDSS/Functional Systems Score (FSS) assessment performed as soon as possible, ideally within 7 days of the onset of symptoms. However, it is not mandatory to perform an EDSS assessment in case of a suspected relapse.

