### 5.1.2.2 Procedures for Recording Adverse Events

Investigator should use correct medical terminology/concepts when recording adverse events in the Adverse Event eCRF. Colloquialisms and abbreviations should be avoided.

Only one adverse event term should be recorded in the event field of the eCRF.

See Appendix 5 for further specific instruction regarding:

- IRRs
- Diagnosis versus signs and symptoms
- Adverse events occurring secondary to other adverse events
- Persistent or recurrent AEs
- Abnormal laboratory values
- Abnormal vital sign values
- Abnormal liver function tests
- Deaths

- All events with an outcome or consequence of death should be classified as serious adverse events and reported to the Sponsor immediately. In certain circumstances, however, suspected adverse reactions with fatal outcome may not be subject to expedited reporting (see Section 5.4). All deaths that occur during the protocol-specified adverse event reporting period, regardless of relationship to study medicine, must be recorded in the Adverse Event eCRF and immediately reported to the Sponsor.
- Worsening of pre-existing medical conditions
- Lack of therapeutic efficacy
- Hospitalization or prolonged hospitalization
- Overdoses, misuses, abuses, off-label use, occupational exposure, or medication error
- Quality defects, falsified medicinal products and product complaints
- Drug interactions

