### 5.1.3 Reporting Requirements from Investigator to Sponsor

# 5.1.3.1 Immediate Reporting Requirements from Investigator to Sponsor

Certain events require immediate reporting to allow the Sponsor and the regulatory authorities to take appropriate measures to address potential new risks associated with the use of the medicine. The investigator must report such events to the Sponsor immediately; under no circumstances should reporting take place more than 24 hours after the investigator learns of the event. The following is a list of events that the investigator must report to the Sponsor within 24 hours after learning of the event, regardless of relationship to study medicine:

- SAEs
- Non-serious adverse events of special interest
- Pregnancy occurred during breastfeeding (for additional information see Section 5.1.3.5)

The investigator must report new significant follow-up information for these events to the Sponsor immediately (i.e., no more than 24 hours after becoming aware of the information). New significant information includes the following:

- New signs or symptoms or a change in the diagnosis
- Significant new diagnostic test results
- Change in causality based on new information
- Change in the event's outcome, including recovery
- Additional narrative information on the clinical course of the event

For reports of serious adverse events and non-serious adverse events of special interest, including follow-up, investigator should record all case details that can be

gathered immediately (i.e., within 24 hours) in the Adverse Event eCRF and submit the report via the electronic data capture (EDC) system. A report will be generated and sent to Roche Drug Safety by the EDC system.

In the event that the EDC system is temporarily unavailable, refer to Section 5.1.3.4.

Investigator must also comply with local requirements for reporting serious adverse events to the local health authority and Institutional Review Board (IRB)/ EC.

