**Table A5-1 Adverse Event Severity Grading Scale** 

Grade	Severity	
Mild; asymptomatic or mild symptoms; clinical or diagnostic observations or intervention not indicated		
2	Moderate; minimal, local, or non-invasive intervention indicated; or limiting age-appropriate instrumental activities of daily living a	
3	Severe or medically significant, but not immediately life-threatening; hospitalization or prolongation of hospitalization indicated; disabling; or limiting self-care activities of daily living b, c	
4	Life-threatening consequences or urgent intervention indicated d	
5	Death related to adverse event d	

NCI CTCAE = National Cancer Institute Common Terminology Criteria for Adverse Events.

Note: Based on the NCI CTCAE (version 5.0), which can be found at: http://ctep.cancer.gov/protocolDevelopment/electronic\_applications/ctc.htm

- a Instrumental activities of daily living refer to preparing meals, shopping for groceries or clothes, using the telephone, managing money, etc.
- b Examples of self-care activities of daily living include bathing, dressing and undressing, feeding oneself, using the toilet, and taking medications, as performed by patients who are not bedridden.
- c If an event is assessed as a "significant medical event," it must be reported as a serious adverse event (see Section 5.1.1.2 for reporting instructions), per the definition of serious adverse event in Section 5.1.1.2.
- d Grade 4 and 5 events must be reported as serious adverse events (see Section 5.1.1.2 for reporting instructions), per the definition of serious adverse event in Section 5.1.1.

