# A5-3.11 HOSPITALIZATION OR PROLONGED HOSPITALIZATION

Any adverse event that results in hospitalization or prolonged hospitalization should be documented and reported as a serious adverse event (per the definition of serious adverse event in Section 5.1.1), except as outlined below.

The following hospitalization scenarios are not considered to be serious adverse events:

- Hospitalization that was necessary because of patient requirement for outpatient care outside of normal outpatient clinic operating hours
- Elective hospitalizations or surgical procedures that are a result of a patient's
  pre-existing condition(s) that have not worsened since receiving trial medication.
  Examples may include, but are not limited to, cholecystectomy for gallstones, and
  diagnostic testing. Such events should still be recorded as medical procedures in
  the concomitant procedures/treatments eCRF
- Hospitalization to receive trial medication such as infusions of ocrelizumab unless this is prolonged (more than 24 hours)

 Hospitalization following an MS relapse as long as the reason for hospitalization is to receive standard treatment with IV methylprednisolone

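### Protocol 4.5.2.5 and the SAP treat a serious MS relapse as a reportable SAE, but Protocol 5.1.1.2 exempts it from the eCRF, so sites have conflicting recording instructions

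*Protocol*

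**What the plan says.** The places that govern how a serious MS relapse is recorded are as follows. Protocol Version 4 (United States) and Version 3 agree on all of them.

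- **Protocol 4.5.2.5, Assessment of Relapses.** Relapses go on a dedicated MS relapse form. "MS relapses should not be reported as an adverse event, unless they are serious".
- **Protocol 5.1.1.2, Specific Adverse Events that are Exempt from Collection.** "Adverse events and serious adverse events related to MS are not considered for recording in the eCRF". Events anticipated as part of MS are recorded as adverse events "only if judged by the physician to have unexpectedly worsened in severity or frequency or changed in nature at any time during the study". A numbered list of events not considered adverse events then opens with MS relapses.
- **Protocol 5.1.1.2, Serious Adverse Events.** Seriousness is defined by the usual criteria, among them "Results in persistent or significant disability/incapacity".
- **Protocol 5.1.3.1.** SAEs are entered in the Adverse Event eCRF and sent to the Sponsor: "under no circumstances should reporting take place more than 24 hours after the investigator learns of the event".
- **Protocol Appendix 5, A5-3.11.** One of the admissions that does not count as an SAE is "Hospitalization following an MS relapse as long as the reason for hospitalization is to receive standard treatment with IV methylprednisolone".
- **Protocol Appendix 5, A5-3.8 and A5-3.10.** The death rule in A5-3.8 refers to A5-3.10 for fatal cases that may escape expedited reporting. A5-3.10 exempts events clearly consistent with the expected progression of the disease, fatal ones included, but asks for an adverse event report when that is uncertain.
- **SAP 4.8.2.** The SAE definition for analysis explicitly includes serious MS relapses. SAEs in mothers are tabulated and listed.

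**The concern.** Two sections of the same protocol tell a site to do opposite things with the same event, and the SAP is written as though only one of them applied. The maternal safety endpoint in Protocol Section 2, Table 1 is the rate and nature of adverse events, and SAEs are the most closely read part of it. If sites follow different sections, maternal SAE data will not be comparable between sites, and some events expected within 24 hours may not be sent. The SAP cannot repair this. SAP Section 4 gives it precedence over the protocol's analyses, but it sets no recording rule for sites and can tabulate only what they enter.

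**Working it through.** The conflict is one of wording, so the check is to apply each rule to the possible kinds of relapse.

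| Relapse | Protocol 4.5.2.5 with A5-3.11 | Protocol 5.1.1.2 exemption | Result |
|---|---|---|---|
| Not serious | Not an AE | Not an AE unless unexpectedly worse or changed | No conflict over seriousness |
| Admitted only for standard IV methylprednisolone, no other criterion met | Admission is not an SAE | Not recorded | Agree |
| Serious on another ground, judged unexpectedly worse or changed in nature | Report as AE, hence SAE | Recorded under the general exception, although the list item has none | Arguably agree |
| Serious on another ground (for example persistent disability, or admission for a different reason), not judged unexpected | Report as AE, hence SAE | Not an AE, not recorded | **Opposite instructions** |

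Four observations show that the last row cannot be read away.

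1. The 5.1.1.2 exemption names serious adverse events, so it cannot be confined to non-serious relapses.
2. In the same list, MRI activity carries an exception for findings that suggest a serious event such as PML. Relapses carry none.
3. The general exception tests whether the event was unexpected or changed in nature. A relapse can meet a seriousness criterion and still be of an expected kind.
4. The A5-3.11 exclusion would be unnecessary if no relapse could be an SAE. It therefore presupposes that some can.

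A5-3.10 adds a further exemption. It does not mention relapses, but an event regarded as clearly expected progression would not be recorded, even if fatal. Its instruction to report uncertain cases helps in part. It does not decide between 4.5.2.5 and 5.1.1.2.

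**Size.** The documents give no count of serious relapses, so no frequency is estimated. One missed SAE can be illustrated for a woman who has no other SAE. The Clopper-Pearson method is an assumption here, taken from the protocol's other proportions.

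- 0/10: upper limit 1 − 0.025^(1/10) = 0.3085, so 0 to 0.308. This agrees with the 0.31 in Protocol 6.2.
- 1/10: lower limit 1 − 0.975^(1/10) = 0.0025. The upper limit solves (1 − p)^10 + 10p(1 − p)^9 = 0.025, giving 0.4450. The width is 0.4450 − 0.0025 = 0.4425, which matches the 0.443 in Protocol 6.2 up to rounding.
- Enrolment is at least 10. With 20 women the step would be from 0/20 (0 to 0.168) to 1/20 (0.001 to 0.249).

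These figures describe any single missed SAE and are not specific to this defect. Protocol 6.6.1 plans 95% CIs for adverse event rates without naming a method. The SAP 4.8.2 outputs name no CI, so the intervals may never be reported.

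**The case against.** The strongest case on the other side is that the intent is clear. The dedicated relapse section, the A5-3.11 exclusion and the SAP definition all assume that serious relapses can be SAEs, which leaves 5.1.1.2 as a drafting slip. Its physician-judgement exception will catch some serious relapses. The eCRF manual and site training mentioned in Protocol 7.2 may already settle practice. 5.1.1.2 also reminds investigators and patients that they can report suspected adverse reactions voluntarily. Relapses remain on the MS relapse form and in the SAP 4.6.3 relapse listing, so a gap can be found. All of this stands, and it limits the consequence. It does not remove the conflict. The text gives no order of precedence between the sections, the manual is not among the documents, and a site that obeys 5.1.1.2 is following the protocol.

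A reader might go further and infer that other protocol rules already force serious relapses into the eCRF. The documents do not support this.

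- *Grade 4 and 5 events must be SAEs (Table A5-1).* That rule grades adverse events. If 5.1.1.2 says a relapse is not an adverse event, the rule is never reached.
- *All deaths must be recorded (5.1.2.2).* The fuller death rule in A5-3.8 refers to A5-3.10, which has its own exemption for fatal disease progression. The death rules therefore lead into another exemption that needs reconciling.

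**Conclusion.** The contradiction is real and is present in both protocol versions. For a relapse that is serious on a ground outside A5-3.11 and is not judged unexpectedly worse or changed in nature, Protocol 4.5.2.5 and SAP 4.8.2 expect an SAE, while Protocol 5.1.1.2 tells the site not to record one. Following 5.1.1.2 removes the event from the Adverse Event eCRF, from 24-hour reporting and from the maternal SAE table.

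The consequence is modest. The co-primary endpoints and the relapse counts do not depend on it, and the relapse form and listing preserve a trace. The number of affected events is unknown and may be zero. The conclusion rests on the protocol and SAP text alone and would matter less if the eCRF manual gives sites a single rule. A reader might infer that maternal SAEs are, or will be, under-reported. The documents show only that the instructions permit it.

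**What to change.** Reconcile Protocol 4.5.2.5, the 5.1.1.2 exemption, A5-3.8, A5-3.10 and A5-3.11, in both Version 4 (United States) and Version 3, together with the SAE definition in SAP 4.8.2, so that one recording rule applies to serious MS relapses. Either direction gives consistency: limit the exemptions to events that are not serious, or take serious relapses out of 4.5.2.5 and out of the SAP definition and align Appendix 5. The sponsor must choose one and state it.

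If serious relapses are to count, compare the relapse listing (SAP 4.6.3) with the SAE listing (SAP 4.8.2) before database lock. Query sites on the seriousness of each relapse against the criteria in Protocol 5.1.1.2, applying the A5-3.11 exclusion. The relapse form alone may not be enough. Nothing shows that it captures seriousness or the reason for admission, and an EDSS at a suspected relapse is not mandatory under 4.5.2.5. Source records may be needed.

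The cost is a wording amendment submitted to the IRB/EC and authorities under Protocol 9.7, a matching SAP edit, a few site queries, and possibly a higher reported maternal SAE count. The comparison of listings is useful even if the amendment comes late.
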